We will use an IRB approved informed consent prior to conducting any study procedures. Since all of the study procedures are telephone-based and we will not have any physical contact with participants, the informed consent process will also occur by telephone. Personnel working remotely from home, will document the date and time of consent and provide their signature using the REDCap electronic-consent feature that implements consent forms through an online survey. This will allow us to keep confidential participant data paper-less and securely saved on Emory's servers. A waiver of written consent document that will be constructed in REDCap has been uploaded for approval.

During the informed consent process, we will describe the purpose of the study, procedures, risks and benefits to participating, compensation, and how confidentiality will be maintained. Since contact information for study PI and Project Coordinator will be provided, a hard copy of the consent form will be mailed to all participants who request it.

POTENTIAL RISKS/DISCOMFORTS TO STUDY PARTICIPANTS AND MEASURES TO PREVENT OCCURRENCE

We will not be discussing any sensitive topics and we do not expect any of the telephone calls, survey questions, or print materials to cause any harm or distress. The primary risk in this study is a loss of privacy or breach of confidentiality. We will take standard measures to protect all participants' confidentiality, as described in the Confidentiality section below. The proposed protocol contains minimal risk so no adverse events are expected. However, should any adverse event occur, the study staff would immediately alert the Principal Investigator (PI), who will have the responsibility of informing Emory IRB.

There are two potential risks for participants in the assessment of implementation study (aim 2), though it is important to stress that the overall risk is judged to be very low. First, study participants may experience risks

related to loss of privacy or breach of confidentiality. Additionally, when participating in the semi-structured interview, they may be hesitant or uncomfortable responding to questions regarding intervention implementation, relevance, barriers experienced, etc. They will be interviewed by staff not directly involved with intervention delivery. We will provide the maximum possible protections so that all participant information is protected and participants understand their rights, data purpose, use, and storage. We will ensure that participants are aware their responses are optional and that they have the right to withdraw from the study at any time without penalty or loss of benefits. Participation will not be disclosed to their organization or anyone outside the research team. All responses will remain confidential and not be shared with anyone except the project staff.

BENEFITS

Participants may benefit from improving their home food environment and/or eating healthier as a result of our intervention materials and contact with health coaches. With participants' help, future 2-1-1 clients and their families may benefit from an intervention that is designed to help them improve their home food environment.

COMPENSATION

Participants will receive a \$40 reloadable gift card (ClinCard) as compensation for completing their baseline data collection (home environment survey and two dietary recalls). An additional \$40 will be loaded to the participant's reloadable gift card after the completion of follow-up 1 and follow-up 2 (HES with 2 dietary recalls at 4-months and 9-months post-baseline). We will also load \$5 to their reloadable gift card if they respond to a text message confirming their contact information at 6-months post-baseline, as a retention strategy. If unable to reach them via text we will mail them a postcard that they will have to initial, confirming their contact information is the same (postcard is included for review). Once we receive the postcard we will load \$5 to their reloadable gift card. The total amount that participants are eligible to receive is \$125, if they complete all parts of this study.

2-1-1 and Horizons leaders and staff in the assessment of implementation study will receive a \$40 Amazon e-card as compensation for taking part in the interview, and intervention arm participants will receive a \$40 Amazon e-gift card or other gift card (e.g., Walmart) as compensation for taking part in the interview (aim 2).

DATA MANAGEMENT AND MONITORING

All study staff, including the PI, will participate in the monitoring of participant data. The proposed protocol contains minimal risk so no adverse events are expected. However, should any adverse event occur, the study staff member who discovered the adverse event would immediately alert the Principal Investigator, who will have the responsibility of informing the Emory IRB. The PI will meet regularly with study staff to ensure that data security is maintained and data analysis is handled as outlined above. Each study participant will be assigned an ID number and surveys will be identifiable via assigned IDs only. A separate Excel database will link identification codes with participants' names. Coaches will upload and store all electronic files, including audio-recordings, on a secure, password protected network drive that is backed up by the RSPH Office of Information Technology.

Data for intervention delivery will be collected via the HHHF Application, a secure electronic intervention delivery application which is hosted on Amazon Web Services (AWS). AWS is a secure cloud services platform, offering database storage, content delivery, and is a more cost-efficient but equally secure platform to host such web-based applications. We have first-hand experience working with AWS and are hosting another web-based application there currently. All other data sources will include hard-copy interview guides with responses, audio files, and tracking logs. All of the electronic files (including data from REDCap) will be stored on the secure network drive and hard-copy files will be locked in a filing cabinet in a locked office only accessible to approved research staff and faculty. While working from home, we are implementing paper-less methods of data collection and tracking.

DATA ANALYSIS

Data Analysis Plan for the hybrid-effectiveness implementation trial

All dietary recalls will be collected, processed, and analyzed using the most recent version of ASA24 that prompts for food description details and automatically codes and calculates nutrient intakes using the USDA Food and Nutrient Database for Dietary Studies.⁶⁹ The ASA24 provides values for total energy, nutrients and nutrient ratios, foods and food groups, and can be used to calculate the HEI to assess diet quality. The ASA24 program provides a daily total for energy intake and other nutrients (e.g., total fat) and food groups (e.g., fruits and vegetables). We will use the average of one weekday and one weekend day to estimate usual short-term diet at each time point.

We will assess continuous outcomes for normality and transform them if assumptions are not met. We will assess missingness of data by conducting logistic regression analyses with reached/not reached for follow-up as the outcome to see if those who were not reached were statistically significantly different from those who were not reached.⁷⁰ Predictor variables will include demographics and other baseline variables such as BMI. For all outcome variables, we will also investigate any outliers and will decide on exclusion if they are unusually high (beyond 3 SD) or impossible values. However, we will make strong efforts to reduce outliers through rigorous data quality control.

To assess the effectiveness of the HH/HF in the 2-1-1 population we will conduct traditional RCT analyses, using both complete case and intent-to-treat data (all participants). We will first assess statistical significance of change between baseline and each follow-up points with appropriate bivariate tests (e.g., independent t-tests, Wilcoxon-Mann-Whitney tests, chi-square tests of independence). We will use growth modeling as the intent-to-treat analysis as it allows for modeling of all available data without the need for multiple imputations based on the assumption of data missing at random.^{71,72} Hence, we will include any variables identified as being related to missingness into these models as covariate. We will utilize multiple imputation if there are issues with missing data for individual covariates.⁷³ In general, growth models will include time (calculated as time elapsed between the measurement point and baseline date) and an interaction effect between time and group assignment. We will assess the intraclass correlation (ICC) due to clustering in 2-1-1 call centers, but based on our previous research, ICCs are expected to be very small (< 1%) and we therefore do not anticipate the need to adjust for clustering. However, if the need arises, we will adjust for clustering using three-level modeling with Bayesian estimators due to the small number of clusters.

Furthermore, we will test differences in intervention effectiveness, i.e., conduct moderator analyses, for demographics/household characteristics, and baseline BMI using growth modeling with interaction effects between group assignment and the moderators of interest. Finally, we will use Structural Equation Modeling to assess changes to the home food environment as mediators as indicated in Figure 4. Data cleaning and analyses will be conducted using SAS 9.4 and Mplus 8.

We will also use the addresses of HH/HF study participants to investigate the relationship between food desert residence and primary and secondary outcome variables such as diet quality and household food inventories. To do so, participants' addresses will be geocoded using ArcGIS 10.8.2 and assigned to 2010 census tract data. These data will then be joined with USDA's Food Access Research Atlas dataset, which includes census tract-level information on food access. Using participant's census tract as an objective indicator of food access de-identifies participants' home locations.

Data Analysis Plan for the assessment of implementation study (aim 2)

Descriptive analyses will be run on survey and coaching log/web analytic data to characterize the process measures and program implementation. Regarding data from 2-1-1 and Horizons leaders and staff, we will conduct analyses pooled across sites and by individual sites (i.e., the four 2-1-1s and Horizons versus EPRC) to understand variations in promotion, recruitment, and implementation. We will also develop a codebook based on evaluation questions and emergent themes from the transcripts. Two analysts will double code each transcript and resolve discrepancies through discussion. NVivo will be used for qualitative data analysis and management. We will then generate code reports using NVivo to facilitate identification of themes and develop matrices to aid in identifying themes and patterns across key categories such as type of 2-1-1 organization (e.g., Atlanta versus Macon/Columbus versus Albany), which differ in terms of staffing structure and organizational and community context. A similar approach will be taken for the analysis of qualitative data from intervention arm participants. The process evaluation data from program participants will be triangulated with the staff interviews to assess multiple stakeholders' perspectives.

Data Analysis Plan for the cost-effectiveness analysis (aim 3)

We will conduct a cost analysis and a cost-effectiveness analysis of the intervention, focusing on effects associated with improvements in diet (i.e., fruit and vegetable consumption, fewer empty calories) and avoidance of weight gain (relative to controls). The analysis will be conducted from the societal perspective and assume a lifetime horizon. We will use estimates of effectiveness of the intervention based on the analysis described above. In the baseline analysis, we will assume that behaviors persist for participants remaining lifetime. We will test the sensitivity of results to reasonable assumptions about effect durability, but most studies linking dietary behaviors to health outcomes in the literature focus on binary classifications of behaviors rather than exposure time. We will build a model that tracks participants from the beginning of the intervention to death. The analysis will conform to Panel on Cost-Effectiveness in Health and Medicine standards for conducting cost-effectiveness analyses.⁶⁸

Direct intervention costs. We will estimate the costs of program delivery in the intervention group. We will not consider costs associated with the evaluation of the intervention. Project staff will be asked to keep time logs to document time spent on developing and delivering the intervention. We will value staff time based on their wages, which are included in the grant budget. For staff who are hired on a full-time basis, we will make a reasonable assumption about the share of time they spend on intervention delivery versus research and value it accordingly. **Indirect costs.** We will record the length of time participants spend on the phone with their Coach and value time using the median US wage. Use of a wage to value time costs is appropriate even for individuals who are not employed because it reflects the opportunity cost of forgone leisure time. **Cost-offsets.** We will focus on the impact of the intervention on fruit and vegetable consumption and obesity. We will follow the methods of Rahkovsky and Gregory to estimate cost-offsets from changes in fruit and vegetable consumption.⁶⁹ They estimate the relationships between food prices and non-high density lipid cholesterol and use their results to predict the impact of interventions to change the consumption of various types of food groups (e.g., vegetables, whole grain products) on cardiovascular disease-related spending. We will use estimates from the nutritional epidemiology literature and estimates of disease-attributable costs, some of which we have estimated,⁷⁰ to predict the impact of dietary changes on cancer- and diabetes-specific costs. We will use a similar approach to estimating cost-offsets from reductions in obesity that occur independently of dietary improvements.

Cost-effectiveness. In the event cost-offsets are lower than the direct costs of the intervention (i.e., it is not cost-saving), we will calculate the incremental cost-effectiveness ratio associated with improvements in health status due to the intervention. The numerator of the ratio is the change in per participant costs between the two groups, including the direct costs of the intervention, indirect costs, and cost offsets. The denominator is the change in quality-adjusted life years.

TRAINING OF THE STUDY TEAM

Intervention staff at both the EPRC and Horizons will include staff who participated in conducting our prior studies on HH/HF. They and newly hired coaches will undergo a two-day in-person training with built-in practice sessions with original program developers and intervention staff. Post-training practice sessions will continue until interventionists are well-versed in interpreting the home environment profile, delivering coaching calls with appropriate tips and goals, and providing effective reinforcement contacts (via text and phone) to reinforce healthy actions and problem-solve challenges. All participant interactions will be audio-recorded until five consecutive coaching sessions and reinforcement calls are delivered successfully. Tailored written and verbal feedback will be provided on all recorded sessions for improvement and audio-recordings will continue for 10% of subsequent calls throughout the duration of the study. Monthly/quarterly group booster training sessions will be held via telephone with all intervention staff to review feedback. Similar processes will be used to train data collection staff with intensive in-person training to be provided by our seasoned study coordinator. Training topics will include item-by-item review of baseline and follow-up surveys, data collection techniques, multiple call attempt tips, and accurate data documentation will be emphasized. Baseline and follow-up survey data will be documented on hard copy and entered into the HH/HF web-based application to generate the home environment profiles. All hard copy survey data will be reviewed for completion (against an

audio recording, if available), and feedback will be provided to data collectors as needed. All hard copy data will be double-entered into an SPSS database to ensure accurate data entry. ASA24 data downloads will also be reviewed regularly and responses requiring revisions will be reviewed by [name] and study faculty. All data collection interactions will be audio-recorded until 5 successful surveys and dietary recalls have been documented with 10% of recalls being recorded thereafter. Ongoing quality control of dietary recall recordings will continue throughout the duration of the study with provision of individual and general group feedback by the study coordinator as needed. All study team members have completed (or will complete once identified) the necessary CITI certifications to maintain human subject protections.

PLANS FOR MONITORING THE STUDY FOR SAFETY

Only authorized study staff will have access to surveys, audio files, transcripts, datasets, information that links identifiers to subjects, and any other information provided. As previously mentioned, all data will be transmitted and saved on a secured research network server of RSPH that can only be accessed by study staff.

All study staff, including the PI, will participate in the monitoring of participant data. The proposed protocol contains minimal risk so no adverse events are expected. However, should any adverse event occur, the study staff member who discovered the adverse event would immediately alert the PI, who will have the responsibility of informing the Emory IRB. The PI will meet regularly with study staff to ensure that data security is maintained and data analysis is handled as described.

CONFIDENTIALITY

Confidentiality of participant data will be protected at all times. The following procedures will take place:

- a) All study personnel will be thoroughly trained on how to maintain confidentiality.
- b) Each participant will be assigned a unique ID number. We will use each participant's ID number instead of his/her name whenever we can, including the surveys and during data analysis. Once the data is exported from the HH/HF Application, we will ensure that all personally identifying information, such as names, will not be stored in the same electronic data file as other study data.
- c) Contact information obtained from participants will be kept on a secure network server. No hard copies of data will be stored.
- d) All data collected will be backed-up on a secure "Research" drive and will only be accessible to CITI certified study staff.
- e) Participant names and other facts that might identify a specific participant will not appear when we present this study or publish its results.
- f) We will use digital recorders and files will be stored electronically on a secure and password protected "Research" drive. Audio files will be deleted once the study procedures and data analyses are complete, or three years after transcription (whichever comes first).

REFERENCES

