x-SIGNIFICANT CHANGE IN DESIRED DIRECTION at $p<.05$. p-values for change between two time points results from independent t-tests and regression analyses; p-values for the ITT analysis are from growth modeling and refer to the significance of the interaction term of group and time

weeks. We did not include the physical activity actions given null results in both the earlier pilot and the main trial.

The majority of participants were African American (82%) and female (74%), with more men participating than expected. Close to half of the participants were unemployed (48%), and just 14% were college graduates with 10% not finishing high school. All participants reported annual household incomes < \$25,000. Typical household size was 2.8 members, and less than half had children in the household (45%). The mean age was 44, and 44% received SNAP benefits. Of the 101 completing baseline data collection, 75% completed the first coaching call, and 51% completed at least four of the six calls. Sixty percent were reached for follow-up one month post-intervention. Outcome measures consisted of the home environment survey used in our prior studies and two 24 hour dietary recalls at baseline and four months. Although not powered to detect change, we observed a significant increase in HEI scores^{14,57} (from 54.5 to 58.9), decreases in Kcal of 203 per day from pre to post, and decreases in self-reported weight of 4 pounds. Consistent with one or both prior evaluations of the HH/HF intervention, we documented significant changes in household food inventories, food shopping behavior, food preparation, family meals from non-home sources (e.g., not eating out or getting take out), and less eating with the TV on. Moderator analyses did not justify targeting the intervention to a specific subpopulation of callers. These results, which documented the feasibility of partnering with 2-1-1 to identify low-income individuals interested in a healthy eating/weight gain prevention intervention, combined with the potential reach of 2-1-1, position us for the current research project.

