To answer our effectiveness and implementation research questions, we will conduct an RCT with follow-up at four months and nine months post-baseline. The four-month post-baseline follow-up will document short-term outcomes and process data such as acceptability of the intervention. The nine-month post-baseline follow-up will assess maintenance of home food environment and dietary changes. Participants will be recruited by United Way of Greater Atlanta 2-1-1 and United Way of SWGA. EPRC staff will obtain informed consent and enroll participants and collect data at baseline and follow-up. Horizons Community Solutions staff will deliver the intervention to participants recruited from outside the Atlanta area and EPRC staff will deliver the intervention to callers from the Atlanta area.

Data Collection Procedures. The telephone interviews will be conducted by trained Emory research staff and graduate research assistants. All data collectors will be blind to group assignment and have no interactions with any intervention delivery related tasks, including mailings. At follow-up, if data collectors are unable to reach participants with the established telephone-based collection protocol, data collectors will text and email participants a unique survey link designed using REDCap for them to complete their home environment survey. A final attempt to collect data will be made via mail. Participants will receive a paper copy of the home environment survey asking them to complete it and mail it back.

Data collectors will be responsible for confirming eligibility of all interested participants referred by 2-1-1 and conducting informed consent to participate in the study. Once verbal informed consent has been documented, the baseline interview will be conducted. Two unscheduled dietary recalls will follow to ensure completion of a weekend and weekday recall for each participant. Similar procedures will be executed for follow-up data collection #1 and #2. Please see table below for data collection and payment schedules.

	Recruitment & Screening	Informed consent	Interview 1 Home Environment Survey	Interview 2 Dietary Recall 1	Interview 3 Dietary Recall 2
Baseline	X	X	\$40		
			X	X	X
Follow-up 1 (4-months post-baseline)			\$20	\$20	
			X	X	X
Follow-up 2 (9-months post-baseline)			\$20	\$20	
			X	X	X

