Dietary recalls will be administered using NCI's web-based application, ASA24. Although this user-friendly application is intended for self-administration, we have also established protocols to aid in researcher-guided telephone-based collection. Additionally, data collectors will be trained on proper probing techniques to ensure all foods, drinks, supplements, and home-made food item ingredients are included. If data collectors are unable to reach participants with the established telephone-based collection protocol at follow-up, data collectors will share the ASA24 study link, username, and password via a text message or an email for participants to complete their 24-hour dietary recalls on their own. **All** participants will receive a copy of their home environment profile and a list of healthy actions at the end of the study.

Baseline and Follow-up Outcome Measures

Primary and Secondary Outcomes/Theoretical Mediators. Our primary outcome will be the USDA Healthy Eating Index (HEI)¹⁴ calculated from two telephone administered 24-hr dietary recalls (one weekday, one weekend day), which will be administered at baseline, four-months, and nine-months post-baseline to estimate total energy intake. Interviewer-administered 24-hr recalls are regarded as the best methodology to measure short-term changes in food intake because they provide high-quality and relatively unbiased dietary data.⁵⁸ Assessment of dietary intake will be conducted under the supervision of [name], MPH, RD. The respondent will be asked to recall all foods and beverages consumed over the previous day, and at each time point two days will be used to estimate average intake. A computer-directed interview process will guide the respondent through several passes to facilitate accurate recall (e.g., meal-based quick list, meal gap review, detailed pass, commonly forgotten foods, final review). Our team used 24-hr dietary recalls in the original trial for HH/HF and the 2-1-1 feasibility study.

Secondary outcomes will include Kcal per day, self-reported weight, and changes to the home food environment, collected at baseline, four-months, and nine-months post-baseline. Covariates include demographic characteristics (e.g., education, income, household composition), as well as food insecurity and depression. We will also collect data on acceptability, relevance and satisfaction from participants.

Randomization

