Participant surveys, completed one month after the intervention will include a number of process evaluation questions. We will ask about receipt of mailed materials, usefulness and relevance of materials, and satisfaction with the coaching calls. Coaches will also complete coaching logs to document goals set and barriers faced or anticipated. Semi-structured interviews will be conducted with four staff at each 2-1-1 (e.g., United Way Director, 2-1-1 director, line agent/resource manager and line agent/community connections specialist) (n=16) and with the Horizons coach and supervisory staff (n=2) via telephone or Zoom. Semi-structured interviews will also be conducted with intervention arm participants based on each of the eight healthy actions (n=45) and based on participants' food security status (n=35) via telephone or Zoom for a total of 80 interviews. Semi-structured interview guides for 2-1-1 and Horizons leaders and staff will cover topics to adoption, adaptation, acceptability, relevance, and maintenance. Semi-structured interview guides with intervention arm participants will cover topics related to barriers and facilitators to healthy action progress and maintenance, barriers and facilitators to healthy food access and healthy eating, and suggestions for program changes or improvements. Interviews will be recorded and transcribed verbatim. All interviews will be conducted by personnel not directly involved in other aspects of the study, to minimize social desirability bias. All study procedures, including the interviews, will occur by telephone. 2-1-1 and Horizons leaders and staff who complete the semi-structured interview will receive a \$40 gift card in appreciation of their time. Intervention arm participants who complete the semi-structured interview will also receive a \$40 e-gift card and/or mailed gift card.

Field Methods for cost-effectiveness study (aim 3)

We will collect program delivery tracking logs, partners' estimated time and costs as part of the cost-effectiveness analysis. We will also include data on call attempts for recruitment, program delivery, frequency and outcome of call contacts, etc. Participant surveys, completed one-month post intervention implementation, will include a number of process evaluation questions that will be used to assess implementation (from aim 1). These data sources will be used for the purposes of program document review to answer evaluation questions.

INFORMED CONSENT PROCESS

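### Coaching-satisfaction items very probably sit in the 4-month telephone survey, listed ahead of the dietary recalls, so a data collector declared blind can learn the arm before taking the primary outcome

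*Combined protocol and SAP*

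**What the plan says.** On blinding, Data Collection Procedures states: "All data collectors will be blind to group assignment and have no interactions with any intervention delivery related tasks, including mailings".

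On process questions, Field Methods for the assessment of implementation (aim 2) states: "Participant surveys, completed one month after the intervention will include a number of process evaluation questions". It then gives their content: "We will ask about receipt of mailed materials, usefulness and relevance of materials, and satisfaction with the coaching calls". Under Control Condition, controls receive two mailings and no coaching.

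The opening of Field Methods for the trial says that the 4-month follow-up "will document short-term outcomes and process data such as acceptability of the intervention". Baseline and Follow-up Outcome Measures adds: "We will also collect data on acceptability, relevance and satisfaction from participants".

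The data collection table lists, at each time point, the home environment survey as Interview 1 and the two dietary recalls as Interviews 2 and 3. The text has the recalls follow the survey at baseline and calls the follow-up procedures similar. Telephone is the first-line mode. The survey link, the paper copy and the self-completed recall are fallbacks for participants who cannot be reached.

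**The concern.** An account of coaching calls identifies the intervention arm. If a data collector asks these items in Interview 1, that collector can lose the blinding that the protocol declares, and may then take the same participant's recalls.

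Those recalls give the HEI and the secondary energy intake. The protocol trains collectors to probe for foods, drinks, supplements and recipe ingredients, and knowledge of the arm can change how hard someone probes. Participants know their own arm and report their own diet, so blinding of the assessor is the protection that the protocol itself claims for these outcomes. If survey and recalls overlap in practice, the claim could not be reported for the primary outcome without qualification.

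**Working it through.** The plan has no stated figure to reproduce here. The check is whether the process survey is the 4-month survey, what follows it, and how many recalls could be involved.

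**1. Timing.** Inputs: a 12-week programme (Intervention Condition, Table 3), a survey one month later (aim 2 field methods) and a follow-up at 4 months post-baseline. One month = 365.25 / 12 / 7 = 4.35 weeks.
- If week 12 is counted from baseline, as in Table 3: 12 + 4.35 = 16.35 weeks, and 16.35 / 4.35 = 3.8 months.
- If the 12 weeks start at the first call, one week after baseline: 13 + 4.35 = 17.35 weeks, and 17.35 / 4.35 = 4.0 months.
- Four months = 4 × 4.35 = 17.4 weeks. Both readings land on or just before Follow-up 1.

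**2. The team's own usage.** The feasibility study also had six calls over three months. Its report says "Sixty percent were reached for follow-up one month post-intervention" and then "Outcome measures consisted of the home environment survey used in our prior studies and two 24 hour dietary recalls at baseline and four months". Both labels describe the same follow-up.

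**3. Other places for the items.** The data collection table has participant interviews only at baseline, 4 months and 9 months. No separate process survey is scheduled. Together with the assignment of process data to the 4-month follow-up, this makes Interview 1 at 4 months the most likely place.

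**4. Order and staffing.** The survey is listed before the recalls. Training of the Study Team mentions surveys and recalls together when it describes how data collectors are checked. That suggests one pool of staff, but it does not say that one person does both for a given participant. No text places the process items after the recalls, makes them self-completed by default, or reassigns a collector who learns the arm. The aim 2 sentence on separate personnel comes within the account of the recorded and transcribed semi-structured interviews and does not cover the participant survey.

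**5. Ceiling on exposure at 4 months.** Planned enrolment is 800, with two recalls each: 800 × 2 = 1,600 recalls. Balanced blocks imply about 800 / 2 = 400 participants allocated to coaching, with 400 × 2 = 800 recalls. Scenarios with retention borrowed from the team's earlier studies, which are assumptions and not bounds:
- 60% (feasibility study): 800 × 0.60 = 480 participants, 960 recalls.
- 82.5% (efficacy trial at six months, with home visits, so less comparable): 800 × 0.825 = 660 participants, 1,320 recalls.

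Surveys or recalls completed by link or on paper lower each figure. No bias or error rate is computed, because the documents give neither a standard deviation for the HEI nor a basis for an assumed bias.

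**The case against.** The strongest reply is that harm needs three links, none of which is stated: a blinded collector asks the items by telephone, asks them before the recalls, and takes that participant's recalls. The questionnaire is not in the documents, so a skip rule, a separate module or a self-completed section cannot be excluded. This stands. It limits the conclusion to what can happen under the plan as written; a reader might infer that the plan shows an actual breach of blinding, and the documents do not support that.

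A reader might also infer that the items always reveal the arm. They do not. In the feasibility study 75% completed the first coaching call, so a participant who reports no calls may be a control or an intervention participant who never started. A description of coaching does reveal the arm.

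The payments do not help to place the survey. The three payments of $40 and one of $5 add up to the stated $125, but that total already leaves out the separate $40 aim 2 interview, so the sum does not show that the process items lie inside Interview 1. The conclusion does not use it.

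Finally, the recalls use a computer-directed sequence of passes and automatic coding, and 10% of them are recorded after the initial check. Participants can also mention their arm in any call. These points limit the likely effect, but they do not replace blinding, and they are no reason to build an arm-revealing question into the call before the recalls.

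**Conclusion.** The point holds as a should-fix, with medium confidence. The plan declares all data collectors blind, very probably puts arm-specific questions in the telephone survey listed before the primary-outcome recalls, and states no safeguard between the two. A collector declared blind can therefore learn the arm before collecting the HEI.

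This rests on three inferences: where the items sit in the survey, that the survey precedes the recalls at follow-up as at baseline, and that one collector may do both for a participant. The ceiling is 800 participants and 1,600 four-month recalls, and the true exposure is lower by an unknown amount.

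Two further readings go too far. One is that the primary result is biased by some calculable amount; the documents give no basis for the number unmasked or the size of any bias. The other is that the 9-month recalls are equally affected; that would need the same collector to be assigned to the participant again, which is not stated.

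**What to change.** Ask the coaching items and any other arm-specific process items only after the second 4-month recall. For participants who do not complete both recalls, ask when the 4-month collection attempts end, so that the aim 2 data are not limited to recall completers. Use the existing REDCap link, or a collector who will take no further recalls from that participant. If the items must stay in Interview 1, put them last and assign the recalls to a different collector.

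Record for each recall whether the collector knew the arm, and qualify the blinding statement in the report if some did. If the tasks are already separated in practice, say so in Data Collection Procedures. If 4-month collection is complete, which the documents do not say, report who asked the process items and who took the recalls.

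The cost is a small protocol amendment, somewhat lower response to the process items because they come later, and mixed-mode aim 2 data if collection has begun. No extra staff are needed when the link is used. The change protects the assessor side only; bias from participants' own reporting remains.
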